**3.2.7 Table Headings**

All analyses will be tabulated by treatment group and include a total if appropriate. The treatment groups are defined as below:

- avapritinib (“ava”) – Data collected during the main study treatment period only from patients randomized\* to avapritinib.
- Regorafenib (“rego”) – Data collected during the main study treatment period only from patients randomized\* to regorafenib.
- avapritinib overall (“ava overall”) – Data collected during both the main and extended study treatment periods from patients randomized\* to avapritinib.

## **Avapritinib**

### **Statistical Analysis Plan Study BLU-285-1303**

- regorafenib to avapritinib (“rego to ava”) – Data collected during the extended study treatment period only from patients randomized\* to regorafenib. During this period, patients are treated with avapritinib after crossing over from regorafenib.

\*For analyses using the Safety Population, patients will be grouped based on the study drug actually received during the main study treatment period rather than the study drug they were randomized to.

Safety, laboratory, exposure, compliance, dose modification, concomitant medications, and major protocol deviation analyses will be presented using the 4 groups above.

Efficacy analyses will be presented using 2 groups (avapritinib, regorafenib).

Analysis populations, patient dispositions, baseline or demographic characteristics, patients by country by site, medical history, and prior therapies for the underlying malignancy will be presented using 3 groups (avapritinib, regorafenib, total).

### **3.3 Methods for Handling Missing Data**

Refer to [Section 7.1](#) for detailed data imputation guidelines.

### **3.4 Windowing of Visits**

Data will be summarized by visit following the visit windows in [Table 1](#) when appropriate (e.g., lab parameters). If multiple assessments occur within a visit window, the assessment closest to the target day will be used. In case of ties, with equal number of days on either side of target day, the value from the day before target day shall be used.

The extended study treatment period will be windowed similarly. The extended study treatment period visits will have a prefix “C”, e.g., C Week 4 (CC2D1).

**Avapritinib  
Statistical Analysis Plan Study BLU-285-1303**

**Table 1: Visit Windows**

Visit	Start day	Target Day	End day
Week 4 (C2D1)	2	29 ± 2	43
Week 8 (C3D1)	44	57 ± 3	71
Week 12 (C4D1)	72	85 ± 3	99
Week 16 (C5D1)	100	113 ± 3	127
Week 20 (C6D1)	128	141 ± 3	155
Week 24 (C7D1)	156	169 ± 7	183
Week 28 (C8D1)	184	197 ± 7	211
Week 4*X (C(X+1)D1)	28*X-12	28*X+1 ± 7	28*X+15

Note: Visit window for Week 4 will not include Day 1 if the Day 1 observation is marked as baseline; X can be 4, 5, 6... until all visit windows are covered. CXDX in parentheses are for calculation purposes and will not be presented in outputs.

### 3.5 Withdrawals, Dropouts, Lost to Follow-Up

Patients may withdraw or be withdrawn from study treatments at any time for any of the following reasons:

- Withdrawal of consent
- Adverse event (AE)
- Disease progression
- Death
- Investigator decision
- Protocol deviation
- Pregnancy
- Lost to follow-up.

### 3.6 Protocol Deviations

All protocol deviations will be entered into the RAVE database by site staff, and their classifications will be entered by designated CRO or sponsor study team members. Details on reporting of protocol deviations can be found in the *Protocol Deviations and Non-Compliance Management Plan*.

Prior to database lock, protocol deviations will be reviewed and categorized as major or minor for summarization.

All major protocol deviations will be tabulated for the ITT Population by treatment.

**Avapritinib**  
**Statistical Analysis Plan Study BLU-285-1303**

A listing of patients with protocol deviations will be provided. A separate listing of patients with major protocol deviations that lead to exclusion from the PP population or any analysis will be provided.

#### **4. STATISTICAL METHODOLOGY**

##### **4.1 Analysis Populations**

A summary of analysis populations by treatment will be presented along with percentages relative to the ITT Population. Derived stratification factors will be tabulated for each factor and all combinations.

- Prior Lines of TKI (2, 3)
- PDGFRA D842V (present, absent)
- Region (Asia, Rest of World)

##### **4.2 Patient Disposition**

The number and percent of patients will be tabulated for the ITT, Safety, PP, and RE Populations, respectively, for the following categories:

- Patients in the population
- Patients who receive study treatment
- Patients who end main study treatment without continuation or cross-over to avapritinib
- Patients who continue or cross-over to avapritinib
- Patients who end treatment after continuation or cross-over to avapritinib
- Patients who receive subsequent anti-cancer therapy

Reasons for treatment discontinuation will be summarized with the following categories collected on the electronic case report form (eCRF):

- Patient refuses treatment
- Withdrawal of consent
- Pregnancy
- Adverse event and related adverse event
- Disease progression (confirmed by Central Review)
- Clinical progression
- Protocol deviation

**Avapritinib**  
**Statistical Analysis Plan Study BLU-285-1303**

- Investigator decision
- Lost to follow-up
- Administrative/Other
- Sponsor decision

Listings will be provided for patients who discontinue treatment with the reason for treatment discontinuation.

Reasons for treatment discontinuation after continuation or cross-over to avapritinib will be similarly summarized.

Reasons for study discontinuation will be summarized with the following categories:

- Withdrawal of consent
- Death
- Lost to follow-up
- Administrative/Other
- Sponsor decision

Listings will be provided for patients who discontinue from study with the reason for study discontinuation.

### **4.3 Demographics and Baseline Disease Characteristics**

Demographic and baseline disease characteristic data will be summarized for the ITT, Safety, PP, and RE Populations. Medical history data will be summarized for the ITT Population.

#### **4.3.1 Demographics**

The number and percentage of patients in each of the following categories will be presented:

- Age group (<65 years or ≥65 years)
- Sex
- Region
- Ethnicity
- Race.

Patients' age (years), height (cm), weight (kg), body mass index (BMI) (kg/m^2), and other continuous demographic variables will be summarized descriptively.

BMI will be calculated as:  $BMI (kg/m^2) = (weight \text{ in kg}) / (height \text{ in m})^2$ .

**Avapritinib**  
**Statistical Analysis Plan Study BLU-285-1303**

**4.3.2 Baseline Disease Characteristics**

The number and percentage of patients in each of the following categories will be presented:

- Mutation Status
  - KIT V654A or T670I (Present, Absent)
  - KIT mutation status in KIT V654A and T670I mutation absent patients (Exon 17 mutation detected, KIT mutation other than exon 17 detected, no KIT mutation detected)
  - Specific Exon 17 mutations (D816X, D820X, N822X, Y823X) in KIT V654A and T670I mutation absent patients
  - PDGFRA D842V
  - PDGFRA non-D842V
- The Eastern Cooperative Oncology Group (ECOG) performance status (0, 1, 2)
- Metastatic disease (Yes, No)
- Largest target lesion size ( $\leq 5$  cm,  $>5$  to  $\leq 10$  cm,  $>10$  cm) by central radiology assessment
- Patient staged at screening by tumor/lymph nodes/metastasis (TNM) system (Yes, No)
- Current stage at screening by TNM
- Prior imatinib (Yes, No)
- Prior sunitinib (Yes, No)
- Primary tumor site of GIST at the time of diagnosis
- Site(s) of metastatic disease
- Prior surgical resection (Yes, No), and type of resection (total, partial, other).

Continuous baseline disease characteristics will be summarized using descriptive statistics.

**4.3.3 Medical History**

Ongoing medical history data will be summarized by system organ class (SOC) and preferred term (PT) per Medical Dictionary for Regulatory Activities (MedDRA) version 18.1. Patients with multiple events coded to the same system organ class or preferred term will only be counted once in the summary for that category.

All medical history data will be listed.

#### **4.4 Prior and Concomitant Medications and Prior Therapies**

Prior and concomitant medications and prior therapies will be summarized for the ITT population.

##### **4.4.1 Prior and Concomitant Medications**

Prior medications are all medications which started and stopped before exposure to study drug. Concomitant medications are all medications taken at any time from the first dose date of study drug to last dose date of study drug + 30 days.

When summarizing data collected only from the main study treatment period, concomitant medications include medications taken at any time from the first dose date of study drug to the earlier of the last dose date of study drug + 30 days or the first dose date of study drug during the extended study treatment period.

When summarizing data collected only from the extended study treatment period, concomitant medications include medications taken at any time from the first dose date of avapritinib during the extended study treatment period to the last dose date of avapritinib + 30 days.

If the last dose date of study drug is not available, then the cutoff date is used in place of the last dose date.

The number and percentage of patients taking concomitant medications and significant non-drug therapies will be summarized and listed by therapeutic area (ATCText3) and preferred drug name. A patient taking the same medication multiple times is counted only once under that preferred drug name.

Prior (with clear flag) and concomitant medications will be listed.

Medications are coded using the World Health Organization Drug dictionary B3 enhanced, version Mar 2019.

##### **4.4.2 Prior Therapies and Surgery Procedures for the Underlying Malignancy**

Prior therapy is defined as all treatment that started and ended on or before first dose date of study drug.

The number and percentage of patients for each category below will be summarized by PT:

- Prior non-TKI Therapy (Yes, No)
- Prior radiation therapy (Yes, No; type (external, brachytherapy or IORT))
- Prior lines of TKIs (2 lines, >2 lines)
- Prior cancer related surgery-procedures (Yes, No)
- Best response to any prior TKI (CR, PR, SD, progressive disease, NE)

## **Avapritinib**

### **Statistical Analysis Plan Study BLU-285-1303**

- Best response to last prior TKI (CR, PR, SD, progressive disease, NE)
- Type of prior surgery procedure (total resection, partial resection or other), and the site of the procedure.

Continuous variables to be summarized include:

- Time between diagnosis and randomization date
- Time between the end of last prior line of anticancer therapy and randomization date
- Duration of previous exposure to TKI

The duration of previous exposure to TKI will be the sum of exposure from each prior TKI therapy, which is number of days from start date to end date captured on the prior cancer therapy eCRF page.

No overlap between the exposure to prior therapies and avapritinib will be allowed and any overlap of exposure will be queried at the data review stage. The end date of the last prior therapy will be imputed as 'Day 1 – 15' if the imputation of partial dates is within 14 days of Day 1. However, if Day 1 of study drug is within the first half of the month, and last prior therapy ended on the same month as study drug start, the day component of last prior therapy end date will be imputed as 1.

#### **4.5 Study Treatments and Extent of Exposure**

Study drug exposure, including the number of doses administered, cumulative dose, dose intensity, relative dose intensity (RDI), duration of treatment, and the proportion of patients with dose modifications will be summarized descriptively by time (every 4 weeks and the overall duration of the data collection period) for the Safety Population.

Day 1 + 28\*(X-1) is the start date of each 4 week period. Day 28 + 28\*(X-1) is the end date of each 4 week period. The end date of last 4 week period is the date of last dose of study drug.

##### **4.5.1 Treatment Duration**

Duration of treatment (days) = (treatment end date – treatment start date + 1).

Duration of treatment (weeks) = (treatment end date – treatment start date + 1) / 7.

The treatment start date is the first dose date of study drug.

For patients receiving avapritinib, the treatment end date is the last dose date of study drug. For patients receiving regorafenib, the treatment end date is the earliest of the last dose date of study drug + 7 days, the data cutoff date, or the death date, to account for the dosing schedule of regorafenib.

For patients with last dose date missing, the earlier of the data cutoff date or the death date will be used.

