### 3.2.2 Day 1 and Other Days

**Date of first dose of study drug (or Day 1)** is defined as the day of the first administration of study drug after enrollment. First dose refers to first dose in study unless otherwise specified.

**Date of first dose of study drug during extended study treatment period (or CC1D1)** is defined as the day of the first administration of study drug after cross-over or continuation post disease progression per central radiology.

**Date of last dose of study drug** is defined as the date of last administration of study drug (last dose) in the study. For patients who have not ended treatment and whose last dose date is missing, the cutoff date will be used. The date of last dose of study drug will be calculated separately for the main study treatment period, the extended study treatment period, and both periods combined.

The **extended study treatment period** (or extended study) is defined as any time on or after CC1D1 in the study.

The **main study treatment period** (or main study) is defined as any time before CC1D1 in the study.

**Day -1** is defined as the day before the first administration of study drug in the study (Day 1).

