**4.5.2 Cumulative Dose**

Cumulative dose (mg) is defined as sum of all doses taken. The dosage will be counted as 0 for days when the study drug is not taken.

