**4.5.4 Dose Intensity**

Dose intensity (mg/day) is defined as the cumulative dose divided by the duration of treatment (in days).

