**4.5.5 Relative Dose Intensity**

Relative dose intensity is defined as the ratio: dose intensity / planned dose intensity. Planned dose intensity is based on initial assigned daily dose.

Relative dose intensity will be summarized both descriptively as a continuous variable and categorically in the following groups: <75%, 75% to <90%, 90% to 120%, and  $\geq 120\%$ .

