#### **4.7.1 Adverse Events**

Adverse Events will be analyzed using treatment-emergent adverse events (TEAEs). The TEAE definition is dependent on the study period (e.g., main study treatment period) reported. An AE is considered a TEAE for a specified study period if the AE occurs during or after administration of the first dose of study drug from the same study period through up to the earlier of the last dose of study drug in that period + 30 days or the day before the start of crossover/extended treatment.

Adverse Event refers to TEAEs unless otherwise specified throughout this document. All AEs will be coded using MedDRA version 18.1. The severity will be graded using the National Cancer Institute (NCI) Common Terminology Criteria for Adverse Events (CTCAE), version 4.03 (patients enrolled before protocol amendment 2) and 5.0.

A patient experiencing multiple AEs under the same PT or SOC will be counted only once for that PT or SOC by maximum severity. If a patient experiences the same AE more than once with more than one causal relationship to study drug, the strongest causal relationship to study drug will be given precedence. Any missing severity, causality, or outcome will not be imputed and classified as 'Missing'. Detailed imputation rules for missing AE dates are in [Section 7.1](#).

The number of patients with at least one AE will be summarized ([Table 4](#)). The following tables summarize incidences of various aspects of AEs and serious adverse events (SAEs):

1. AE Summary (including all subsequent items)
2. AE by PT
3. AE by SOC and PT
4. AE related to study drug by PT
5. AE related to study drug by SOC and PT
6. SAE by PT
7. SAE by SOC and PT
8. SAE related to study drug by PT
9. SAE related to study drug by SOC and PT
10. Grade 3/4/5 AE by PT
11. Grade 3/4/5 AE by SOC and PT
12. Grade 3/4/5 AE related to study drug by PT
13. Grade 3/4/5 AE related to study drug by SOC and PT
14. AE by PT and NCI CTCAE Grade
15. AE by SOC, PT, and NCI CTCAE Grade

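### SAP 4.5.1 and 4.4.1 carry a stopped patient with no last-dose date on to the data cutoff (or, in 4.5.1, death if sooner), which overstates treatment duration and can understate dose intensity

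*SAP*

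**What the plan says.** Three places in the SAP deal with a missing last-dose date.

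- SAP 3.2.2, the general definition: "For patients who have not ended treatment and whose last dose date is missing, the cutoff date will be used". It gives no substitute for a patient who has ended treatment. It also has the date worked out separately for the main period, the extended period and both combined.
- SAP 4.5.1, for treatment duration: "For patients with last dose date missing, the earlier of the data cutoff date or the death date will be used". The condition about not having ended treatment is absent.
- SAP 4.4.1, for concomitant medications: "If the last dose date of study drug is not available, then the cutoff date is used in place of the last dose date". The condition is absent here too.

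In SAP 4.5.1 the avapritinib end date is otherwise simply the last dose: "For patients receiving avapritinib, the treatment end date is the last dose date of study drug". For regorafenib it is the last dose plus 7 days, or the cutoff or death if sooner. Duration in days is then the denominator of dose intensity (SAP 4.5.4), whose numerator is cumulative dose. For that numerator, SAP 4.5.2 says: "The dosage will be counted as 0 for days when the study drug is not taken". RDI follows in SAP 4.5.5: "Relative dose intensity is defined as the ratio: dose intensity / planned dose intensity".

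The treatment-emergent adverse event window in SAP 4.7.1 closes at "the earlier of the last dose of study drug in that period + 30 days or the day before the start of crossover/extended treatment". SAP 4.7.4 likewise ties on-treatment deaths to the last dose plus 30 days.

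**The concern.** Once SAP 3.2.2 has been applied, a patient still on treatment already has the cutoff as last-dose date. The only patients left for the missing-date sentence in SAP 4.5.1 are those who have stopped, and for them the cutoff is the wrong end of treatment. Both SAP 3.5 and SAP 4.2 list loss to follow-up and withdrawal of consent as reasons for stopping, so such patients are foreseeable.

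For them, drug-free days enter the duration. If cumulative dose holds only the recorded doses, those days enter the denominator of dose intensity and not the numerator. What is at stake is the descriptive exposure comparison between arms in the Safety Population, and consistency: two programmers working from different sections would treat the same patient differently.

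**Working it through.** The plan states no exposure figure and no count of missing last-dose dates, so there is nothing of its own to reproduce. The check sets the rules side by side and then applies the SAP's formulas to assumed dates.

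**Rules for a patient who has stopped and has no last-dose date**

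| Use | Section | Result |
|---|---|---|
| General last-dose date | SAP 3.2.2 | No substitute given |
| Treatment duration, hence dose intensity and RDI | SAP 4.5.1 | Cutoff, or death if sooner |
| Concomitant-medication window | SAP 4.4.1 | Cutoff |
| Treatment-emergent AE window | SAP 4.7.1 | Relies on last dose; undefined |
| On-treatment deaths | SAP 4.7.4 | Relies on last dose; undefined |

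**One patient**

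Inputs: 300 mg once daily (Protocol 6.3). Assumed: 60 days of dosing, then loss to follow-up; alive; cutoff at Day 548; only recorded doses counted.

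- Cumulative dose = 300 × 60 = 18,000 mg.
- Duration = end − start + 1. Actual: 60 days = 60/7 = 8.6 weeks. Under SAP 4.5.1: 548 days = 548/7 = 78.3 weeks.
- Dose intensity = cumulative dose / duration. Actual: 18,000/60 = 300 mg/day. Under SAP 4.5.1: 18,000/548 = 32.8 mg/day.
- RDI = dose intensity / 300. Actual: 100%. Under SAP 4.5.1: 10.9%. The patient drops from the 90% to 120% category to the one below 75%.
- Other assumed cutoffs: Day 365 gives 60/365 = 16.4%; Day 730 gives 60/730 = 8.2%.
- If the patient had instead died on Day 200, the death cap would give 18,000/200 = 90 mg/day, RDI 30%.

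Over a wider assumed grid (stop on Day 28, 84 or 150; cutoff on Day 180, 365 or 730), RDI runs from 28/730 = 3.8% to 150/180 = 83.3%, with 702 to 30 excess days.

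**One arm of 230**

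- Shift in mean duration = k × (548 − 60)/7/230, where k is the number of affected patients. k = 1 gives 0.30 weeks; k = 2 gives 0.61 weeks.
- A second set of assumptions: complete-data mean RDI 90%, other patients treated for 150 days, affected patients stopping at Day 84 with cutoff at Day 365. Two affected patients give mean RDI (228 × 0.9 + 2 × 0.9 × 84/365)/230 = 89.4%. Twelve give 86.4%, with mean duration 161.2 days against a true 146.6.

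**If the imputed date also closes the dosing record**

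Cumulative dose becomes 300 × 548 = 164,400 mg and RDI stays at 100%. The error then lies in cumulative dose and duration. SAP 4.5.2 does not say how an open dosing record is closed.

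**The case against.** The best case on the other side is that this is a wording mismatch with little behind it, and that the wider consequences a reader might infer do not follow. Most of that stands.

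- **The adverse-event window.** A reader might infer that adverse events up to the cutoff would count as on treatment. The documents do not support this. SAP 4.7.1 relies on the last dose of study drug, not on the treatment end date of SAP 4.5.1, and SAP 3.2.2 withholds the cutoff from patients who have stopped. The window is undefined, not extended. In addition, Protocol 9.4 generally ends collection 30 days after the last dose (related serious events continue), and the listed AE tables count patients, so no incidence uses this denominator.
- **Concomitant medications.** SAP 4.4.1 does extend this window to the cutoff. However, Protocol 7.2.7 records medications only to 30 days after the last dose, and a patient lost to follow-up supplies little afterwards.
- **Crossover.** A reader might infer that regorafenib duration would run on through avapritinib treatment. SAP 4.5.1 has no explicit cap at crossover. But SAP 3.2.2 computes last dose by period, SAP 3.2.7 confines the regorafenib column to the main period, and SAP 4.4.1 caps the main-period medication window at the start of extended treatment. The washout of 7 to 28 days required by Protocol 7.6 cannot be confirmed without the last regorafenib date. This case is largely answered.
- **Frequency.** The 2% dropout in the sample-size section is an input to the PFS calculation, not a rate of missing dosing dates, and cannot be used to predict how many patients are affected.
- **Logical dates.** SAP 7.1 requires imputed dates to be logical, but its example is death only. It does not clearly override SAP 4.5.1 for a living patient who has stopped.

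What the objection does not remove is the sentence in SAP 4.5.1. Followed literally, it gives a wrong exposure figure.

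**Conclusion.** The point holds as a minor correction. For a patient who has stopped with no last-dose date, SAP 4.5.1 counts time to cutoff or death as treatment, against the condition in SAP 3.2.2, and SAP 4.4.1 does the same with the cutoff for concomitant medications. Duration is overstated. Dose intensity and RDI are understated, provided that cumulative dose counts only recorded doses.

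The error can be large for one patient (RDI 10.9% instead of 100% in the illustration) and small for an arm (about 0.3 to 0.6 weeks of mean duration for one or two patients). Both figures rest on assumed stop and cutoff dates, and the number affected is unknown. The treatment-emergent AE and on-treatment-death windows have a gap for these patients, not an extension. PFS, ORR, OS and the Type I error are untouched.

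**What to change.** In SAP 4.5.1 and 4.4.1, limit the cutoff rule to patients still on treatment, as SAP 3.2.2 already does. Add one rule, best placed in SAP 3.2.2, for patients who have ended treatment in a period and have no last-dose date. It should use the last documented dosing or drug-accountability date in that period, no later than the treatment discontinuation date, the day before CC1D1 (for the main period), death or the cutoff. Apply that one date to duration, the treatment-emergent AE window, on-treatment deaths and the concomitant-medication window.

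The cost is two amended sentences, one added rule and a small programming change. No new data are needed: Protocol 8.2 already requires dated accountability records, and SAP 4.5.7 already summarizes pills dispensed and returned.
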